6.2.3 Ablation Procedure

The investigator should follow the site's standard practice for the ablation procedure. The type of ablation should be recorded in the eCRF.

Type of Ablation

- Radiofrequency
- Cryoablation

6.2.4 Vessel Closure with Perclose SMC

The investigator should follow site standard practice for the closure procedure using Perclose SMC. All access sites are planned to be treated with Perclose SMC. In the case only post-close technique is used, the subject is considered to be registered in this study at the point the first Perclose SMC is inserted into the body (proximal tip of the Perclose SMC crosses the distal end of the sheath).

The investigator should record the following information for each access site.

- Procedure start and end time
- Closure technique (pre-close or post-close)
- Number of Perclose Device used and Number of sutures deployed
 - o Planned
 - Additional
 - If Perclose SMC is inserted, but suture cannot be deployed, it is still included in the number of Perclose devices used but is not included in the number of sutures deployed)
 - If such a case happens, it must be recorded as the device malfunction in the CRF, as well as reporting as a device malfunction to Abbott PPG.

Study Name: Perclose Multi-Access DUS Trial

Clinical Investigation Plan

- Additional hemostat procedure used
 - Manual compression
 - o Tissue stitch
 - Use of other closure devices (specify)
 - Conversion to surgical cut-down
- DUS-guided closure technique
- Time to Hemostasis
 - Per access site
 - Defined as the time from the suture knotting to the time of hemostasis achieved at each access site
 - o Per subject
 - Defined as the time from the first suture knotting to the time of the final hemostasis achieved of all access sites

If the investigator encounters any device malfunctions, even though prior to use, they must be recorded in the eCRF (for registered subjects) and must be reported to Abbott PPG.

6.2.5 Heparin Reversal

If heparin reversal is done, it should be recorded in the eCRF.

6.3 **Post-Procedure**

Post-procedure subject management to discharge should be per the site standard. The investigator should record:

- Time to mobility (time to remove leg movement restrictions while patient is in bed)
- Time to ambulation (time to move outside the bed)

6.4 Discharge (Complication Assessment)

At the time of discharge, the investigator should assess whether the subject has symptomatic or visible access site complications. In addition, femoral DUS must be done per the Corelab Guideline in the leg or legs in which access sites were closed in all subjects registered in this study to detect asymptomatic/non-visible complications if they exist. If a complication is treated, it should also be recorded in the eCRF.

DUS images should be uploaded for Corelab analysis per Abbott's specified method within 7 days from the procedure. The core laboratory will review the images and provide their assessment to investigators to determine whether 30-day DUS is required.

The investigator should record:

- Time of DUS
- Time of Discharge

Study Name: Perclose Multi-Access DUS Trial

Clinical Investigation Plan

Access site complications:

- Femoral vein stenosis (> 50%) development at the puncture site related to closure technique
 - Requiring surgical or percutaneous repair
 - Not requiring surgical or percutaneous repair
- Deep vein thrombosis in the target limb
 - Requiring surgical or percutaneous repair
 - Not requiring surgical or percutaneous repair
- Venous bleeding, retroperitoneal bleeding
 - Requiring surgical or percutaneous repair
 - Not requiring surgical or percutaneous repair
- Venous access site injury including vessel laceration
 - Requiring surgical repair, angioplasty, stenting, ultrasound-guided compression or thrombin injection
 - Not requiring above
- Re-bleeding at the access site
 - Requiring treatment or re-hospitalization
 - Not requiring treatment or re-hospitalization
- Hematoma
 - Requiring surgical or percutaneous repair
 - Hematoma \geq 6 cm but not requiring transfusion or surgical intervention
 - None of above
- Pseudoaneurysm
 - Requiring surgical or percutaneous repair
 - Requiring thrombin injection, fibrin adhesive injection, or ultrasound-guided compression
 - Not requiring above
- AV fistula
 - Requiring surgical or percutaneous repair
 - Not requiring surgical or percutaneous repair
- Venous tear
 - Requiring surgical or percutaneous repair (major)
 - Not requiring surgical or percutaneous repair

- Venous perforation
 - Requiring surgical or percutaneous repair (major)
 - Not requiring surgical or percutaneous repair
- Arterial tear
 - Requiring surgical or percutaneous repair (major)
 - Not requiring surgical or percutaneous repair
- Arterial perforation
 - Requiring surgical or percutaneous repair (major)
 - Not requiring surgical or percutaneous repair
- Infection
 - requiring oral, intramuscular, or intravenous antibiotics, or leading to a prolonged hospitalization (major)
 - Not requirng above (minor)
- No flow-limiting suture material
- Access site-related nerve injury
 - Persisting for > 30 days
 - Resolved \leq 30 days
- Pulmonary embolism
 - Requiring surgical or endovascular intervention and/or resulting in death, to be confirmed by CT pulmonary angiography, lung ventilation/perfusion scan (VQ scan), or autopsy
 - Not requiring or resulting above
- Other

6.5 30-day Follow-up Assessments

All subjects registered in the study must have follow-up assessments at 30 days (+/- 7 days).

If a subject has any access site-related vascular complications (either symptomatic/visible or asymptomatic/nonvisible), nerve injury, or infection at discharge, the follow-up must be done by a site visit. For those subjects who had vascular complications detected on femoral DUS at discharge, a repeat femoral DUS must be done at the 30-day visit in the leg or legs in which the vascular complication(s) was (were) found at discharge.

For a subject who does not have an access site-related vascular complication, nerve injury, or infection, 30-day follow-up can be done by telephone contact. The investigator or the designee should ask whether the subject has any signals of vascular complications. If the subject has a

susceptive signal, he/she is asked to visit the hospital for further assessment, and this site visit is regarded as the 30-day follow-up. If the telephone contact is done within the time window, it is not regarded as the deviation even though the site visit occurs outside of the window.

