3.2 Measures Taken to Avoid and Minimize Bias

The independent DUS core laboratory is used to assess DUS-detected vascular complications to avoid inter-site bias.

Study Name: Perclose Multi-Access DUS Trial

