4.0 ENDPOINTS

4.1 Primary Endpoints and Rationale

The primary endpoint of this study is:

• Vascular complications detected by scheduled DUS at discharge or 30 days in asymptomatic/non-visible complication subjects

In real-world practice, femoral DUS is not routinely done in ablation procedures and only done when access site-related complications are visible (such as hematomas) and/or symptomatic. Therefore, a scheduled femoral DUS in asymptomatic or non-visible complication subjects will support the overall safety of Perclose SMC in multiple access site closures in a single vein. Any visible and/or symptomatic access site-related complications will be also be captured but will be excluded from the primary endpoint analysis.

The primary endpoint is further categorized as major or minor. Major complications are defined as those which require surgical, interventional, or pre-specified repair and/or hospitalization. All other complications are considered to be minor complications.

Vascular access site-related complications include, but are not limited to:

- Femoral vein stenosis (> 50%) development at the puncture site related to closure technique
 - Requiring surgical or percutaneous repair (major)
 - Not requiring surgical or percutaneous repair
- Deep vein thrombosis in the target limb
 - Requiring surgical or percutaneous repair (major)
 - Not requiring surgical or percutaneous repair

Study Name: Perclose Multi-Access DUS Trial

- Venous bleeding, retroperitoneal bleeding
 - Requiring surgical or percutaneous repair (major)
 - o Not requiring surgical or percutaneous repair
- Venous access site injury including vessel laceration
 - Requiring surgical repair, angioplasty, stenting, ultrasound-guided compression, or thrombin injection (major)
 - Not requiring above
- Re-bleeding at the access site
 - Requiring treatment or re-hospitalization (major)
 - Not requiring treatment or re-hospitalization
- Hematoma
 - Hematoma \geq 6 cm
 - Requiring surgical or percutaneous repair (major)
 - Not requiring surgical or percutaneous repair
- Pseudoaneurysm
 - Requiring surgical or percutaneous repair (major)
 - Requiring thrombin injection, fibrin adhesive injection, or ultrasound-guided compression (major)
 - Not requiring above
- Arteriovenous (AV) fistula
- Venous tear
 - Requing surgical or percutaneous repair (major)
 - Not requiring surgical or percutaneous repair
- Venous perforation
 - Requiring surgical or percutaneous repair (major)

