 - Not requiring surgical or percutaneous repair
- Arterial tear
 - Requiring surgical or percutaneous repair (major)
 - o Not requiring surgical or percutaneous repair
- Arterial perforation
 - Requiring surgical or percutaneous repair (major)
 - Not requiring surgical or percutaneous repair

• Other Complications found by DUS

DUS images will be analyzed by the independent DUS core laboratory and used for the primary endpoint analysis (**complications with bold face**). Investigators are also required to assess DUS detected complications, but the core laboratory is blinded to the site's assessment.

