5.0 SUBJECT SELECTION AND WITHDRAWAL

5.1 Subject Population

This clinical study will register subjects of all genders who are planned to have elective ablation procedures requiring multiple vein access sites in a single femoral vein. Subjects must meet all eligibility criteria and provide written informed consent prior to registration in this study. Although complications are collected from all registered subjects, primary endpoint analysis is performed only in subjects with asymptomatic/non-visible complications, as the objective of this study is to understand asymptomatic/non-visible complications only observed by DUS.

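### The symptomatic/visible label that removes a complication from the primary analysis need not be recorded before the investigator sees the discharge ultrasound

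*Combined protocol and SAP*

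**What the plan says.** The primary endpoint in Section 4.1 is "Vascular complications detected by scheduled DUS at discharge or 30 days in asymptomatic/non-visible complication subjects". The same section adds: "Any visible and/or symptomatic access site-related complications will be also be captured but will be excluded from the primary endpoint analysis". Section 5.1 states the restriction by subject: "primary endpoint analysis is performed only in subjects with asymptomatic/non-visible complications".

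The only assessor of symptomatic or visible status that the text names is the investigator, in Section 6.4: "At the time of discharge, the investigator should assess whether the subject has symptomatic or visible access site complications. In addition, femoral DUS must be" performed in all registered subjects. The second of these sentences adds the femoral DUS without giving an order. Under the items to record, the section lists a time for the DUS and a time for discharge, but none for the clinical assessment.

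On who sees the scan, Section 4.1 says "Investigators are also required to assess DUS detected complications, but the core laboratory is blinded to the site's assessment", and Section 6.4 says "The core laboratory will review the images and provide their assessment to investigators to determine whether 30-day DUS is required". The bias control offered in Section 3.2 is: "The independent DUS core laboratory is used to assess DUS-detected vascular complications to avoid inter-site bias".

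**The concern.** A primary event needs two facts: a complication on the scheduled DUS, and the absence of a symptomatic or visible complication. The first is read by a core laboratory blinded to the site. The second is a bedside judgement, and the person who makes it must also read the scan.

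Section 5.1 says the study exists to understand complications that only DUS reveals. That requires a clinical examination made without knowledge of the scan. A site that follows Section 6.4 as written could instead examine the groin with the DUS result in view. No bad faith is needed: a collection on the scan invites a closer look, and slight swelling or bruising may then be noted that would otherwise have been passed over. The lesion then leaves the primary count. A scan without a finding has nothing to move in the other direction, so any relabelling lowers the primary rate.

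**Working it through.** **Does any provision fix the order or protect the label?**

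- Section 6.4 mentions the clinical assessment first and the DUS second. That is the order of two sentences, not a requirement.
- The blind in Section 4.1 runs one way: the core laboratory does not see the site's reading. The site is not blinded to the scan.
- Section 3.2 names only the core laboratory, which addresses the DUS finding.
- Section 10.8 has the CEC adjudicate the Section 4.2 complications and their relation to the closure procedure and device. Symptomatic or visible status is not named.
- Appendix II defines the complications but not the words symptomatic or visible.
- Section 11.3 asks for dated and signed visit notes. A date alone does not order two events at one visit.

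**Size.** The plan states no expected rate that can be read, so there is no figure of its own to reproduce. Inputs: N = 35 (Section 3.0); x = DUS-positive subjects without a sign noted before the scan, assumed to be 1 to 4; m = the number relabelled, also assumed. For simplicity no other subject is excluded.

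If relabelled subjects leave numerator and denominator (the Section 5.1 reading), the primary rate falls from x/35 to (x − m)/(35 − m). The fall is

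x/35 − (x − m)/(35 − m) = m(35 − x) / [35(35 − m)],

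or (35 − x) / [35(35 − m)] per relabelled subject.

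- Smallest: x = 4, m = 1 gives 31/(35 × 34) = 31/1190 = 2.6 points.
- Largest: m = x gives 1/35 = 2.9 points.

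If exclusion is by complication and the denominator stays at 35 (the Section 4.1 reading), each relabelled subject costs 1/35 = 2.9 points.

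Illustrations with exact (Clopper-Pearson) 95% intervals:

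| x | None relabelled | One relabelled | Two relabelled |
|---|---|---|---|
| 1 | 1/35 = 2.9% (0.1 to 14.9) | 0/34 = 0% (0 to 10.3) | not applicable |
| 2 | 2/35 = 5.7% (0.7 to 19.2) | 1/34 = 2.9% (0.1 to 15.3) | 0/33 = 0% (0 to 10.6) |
| 3 | 3/35 = 8.6% (1.8 to 23.1) | 2/34 = 5.9% (0.7 to 19.7) | 1/33 = 3.0% (0.1 to 15.8) |
| 4 | 4/35 = 11.4% (3.2 to 26.7) | 3/34 = 8.8% (1.9 to 23.7) | 2/33 = 6.1% (0.7 to 20.2) |

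The two denominators give point estimates that differ by at most about 0.4 points (for example 2/33 = 6.1% against 2/35 = 5.7%).

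**What does not move.** Section 6.4 requires the discharge DUS in all registered subjects, and Section 3.0 sends all images to the core laboratory. The label therefore does not alter the total of DUS-detected complications. A relabelled event is still reported under Section 4.2 and recorded as an adverse event under Section 7.0.

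**The case against.** The best defence has five parts.

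1. **The text does not say who makes the final primary classification.** Section 4.1 excludes symptomatic or visible complications without naming a decider. The text under Section 8.1 (Analysis Population) is not readable in the copy reviewed, and the CEC charter, Corelab Guideline and case report forms were not supplied. Any of these might set the order or name an arbiter. This stands, and limits the point to the readable text.
2. **An independent committee exists.** A relabelled event would fall within the CEC's remit. This stands in part: the CEC would review the complication, but its stated task does not include whether the sign was noted before the scan.
3. **The order might be recoverable.** A reader might infer from the two listed times that the sequence could never be reconstructed. The documents do not support that. The list in Section 6.4 is not shown to be the whole case report form, Section 11.3 requires visit notes, and Section 11.0 provides a time-stamped audit trail of data entry. These might show the order, but none guarantees it.
4. **The event is not lost.** A reader might infer that relabelling favours the device. That is not established: the silent count falls by one, but the overt count rises by one, and an overt complication is not plainly the better result.
5. **The mechanism is narrow.** A closer look at the groin could make a hematoma visible. It is much less likely to do so for a vein stenosis or an arteriovenous fistula. This stands.

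In addition, Sections 8.6 and 8.7 plan no hypothesis test and no success criterion, so no error rate or pass/fail decision is at stake.

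**Conclusion.** The point holds as a modest design weakness with a cheap remedy. The readable text lets the investigator assign the symptomatic/visible label with the DUS in view, and neither the core-laboratory blind nor the CEC's stated remit covers that step. The consequence is a possible downward bias in the silent-complication rate of about 2.6 to 2.9 percentage points per relabelled subject, assuming 1 to 4 DUS-positive subjects among 35. The total DUS-detected count is unaffected.

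The documents show that relabelling is possible, not that it will happen. A reader might take from the table that the primary rate would be halved. That would be a product of the assumed counts (two of four relabelled), not something the plan implies. The conclusion would change if the CEC charter, Corelab Guideline or case report forms already require a clinical assessment recorded before the scan; a reference to that rule in Section 6.4 would then be enough for discharge.

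**What to change.** 1. **Section 6.4:** require the symptomatic/visible assessment to be completed and recorded, with its time, before the discharge DUS images are viewed. Add the time of the access-site clinical assessment to the recorded items.
2. **Section 4.1:** define discharge symptomatic/visible status by that pre-DUS record. A complication that the core laboratory finds on the scheduled discharge DUS, and that the record did not note, stays in the primary endpoint even if a sign is noted later. A complication that arises after a scan without that finding remains symptomatic/visible. The second half is needed so that overt events following a negative scan do not enter a silent-complication endpoint.
3. **Section 6.5:** at a 30-day visit with DUS, record the clinical assessment before that DUS is viewed. The investigator will already know the discharge result, so this protects only against the 30-day images.
4. **Section 8.2:** report all core-laboratory DUS-detected complications over all registered subjects beside the primary count. This figure does not depend on the label.

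The cost is a few sentences and one time field on the case report form, with no added subjects or procedures. The downside is that sites must do and time the groin check before viewing the scan. The change should be made before data collection, since nothing in the readable text guarantees that the order can be established afterwards.

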4.2 Descriptive Endpoints

Any vascular complications and access site complications will also be analyzed as the descriptive endpoints. Vascular complications include but are not limited to:

- Femoral vein stenosis (> 50%) development at the puncture site related to closure technique
- Deep vein thrombosis in the target limb
- Venous bleeding, retroperitoneal bleeding
- Venous access site injury including vessel laceration
- Re-bleeding at the access site
- Hematoma
- Pseudoaneurysm
- AV fistula
- Venous tear
- Venous perforation
- Arterial tear
- Arterial perforation
- Infection
 - requiring oral, intramuscular, or intravenous antibiotics, or leading to a prolonged hospitalization (major)
 - Not requring above (minor)
- Non-flow limiting suture material
- Access site-related nerve injury
 - Persisting for > 30 days (major)
 - Resolved \leq 30 days
- Pulmonary embolism

- Requiring surgical or endovascular intervention and/or resulting in death, to be confirmed by CT pulmonary angiography, lung ventilation/perfusion scan (VQ scan), or autopsy (major)
- \circ Not requring or resulting above
- Other (specify)

Procedural information listed below will also be analyzed.

- Procedure duration
- Type of Procedure (Cryo-ablation, RF ablation, etc.)
- Number of Femoral Vein Access Sites Per Subject
- Number of Femoral Vein Access Sites Per Leg
- Sheath Sizes Used
- Total Number of SMC used
- Number of SMC used per closure procedure
- Number of SMC used per access site
 - Number of SMC used for > 8F access site
- Number of SMC used per leg
- Device Success rate per access site
 - Successful hemostasis without surgical conversion, or additional non-study device (adjunctive manual compression and subcutaneous stitch are regarded as the standard of care and not included as failure)
- Anticoagulant and antiplatelet medications
- Use of protamine for heparin reversal

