5.6 Number of Subjects

A total of 35 subjects will be registered in the clinical study. Of these,

- 8 subjects will be treated with two Perclose SMC for a single access site closure > 8F.
- 12 subjects will have 3 or 4 access sites in a single vein.

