7.0 ADVERSE EVENTS

All vascular complications must be recorded as adverse events. In addition to vascular complications, serious adverse events (SAE) and device-related adverse events (adverse device effect) must be recorded in the CRF. Any Device Deficiency/Device Malfunction must also be recorded. Additional reporting criteria are listed under 7.3 Adverse event reporting.

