7.3 Adverse Event and Device Deficiency/Device Malfunction Reporting

7.3.1 Adverse Event (AE) Reporting

In this study, all vascular complications (regardless of the seriousness), all serious adverse events, procedure-related adverse events, and adverse device effects related to Perclose SMC must be reported.

Safety surveillance and reporting starts when the first Perclose SMC enters the subject's vasculature and will continue until a 30-day follow-up visit has been performed, unless the subject is deceased, or the subject withdraws from the clinical study. Adverse events will not be collected on de-registered subjects (unless specifically required by the CIP or requested by the regulatory authority). Safety surveillance and reporting will continue until sites perform the last follow-up visit, the subject is deceased, the subject concludes participation in the clinical investigation, or the subject withdraws from the clinical investigation. Sites will collect all adverse event data, including deaths and device deficiency data (if applicable), throughout the period defined above and will report these events to the Sponsor on a CRF. Sites should update additional information regarding an adverse event on the appropriate CRF.

Unchanged, chronic, non-worsening, or pre-existing conditions are not AEs and should not be reported.

The investigator must report all SAEs to the Sponsor as soon as possible but no later than outlined below.

Clinical Site	Reporting timelines
All Sites	SAEs must be reported to the Sponsor no later than 3 calendar days
	from the day the site personnel became aware of the event or as per the investigative site's local requirements, if the requirement is more stringent than those outlined above.

The Sponsor will provide an offline form to allow the investigator to report SAEs in the event the entry cannot be made in the Electronic Data Capture (EDC). This does not replace the EDC reporting system. Sites should still enter all information in the EDC system as soon as feasible.

The date the site staff became aware the event met the criteria of an SAE must be recorded in the source document. The Investigator will further report the SAE to the local IRB according to the institution's IRB reporting requirements.

Adverse Device Effect (ADE)

An adverse event related to the use of an investigational medical device.

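### The stated 30-day telephone question covers only vascular complications, so post-discharge infection and nerve injury, both descriptive endpoints, may go unelicited in subjects followed by telephone

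*Combined protocol and SAP*

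**What the plan says.** Section 6.5 requires a 30-day assessment (± 7 days) in every subject. A vascular complication, nerve injury or infection at discharge means a site visit. For the others: "For a subject who does not have an access site-related vascular complication, nerve injury, or infection, 30-day follow-up can be done by telephone contact". The content of that call is one sentence: "The investigator or the designee should ask whether the subject has any signals of vascular complications". A suspicious answer leads to a hospital visit, which then counts as the 30-day follow-up.

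Section 4.2 lists infection, access site-related nerve injury and pulmonary embolism among the descriptive endpoints. Infection is graded major when "requiring oral, intramuscular, or intravenous antibiotics, or leading to a prolonged hospitalization (major"; nerve injury is graded major when it lasts more than 30 days. Section 6.4 sets out the full complication list, but for discharge.

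On adverse events, 7.0 says: "In addition to vascular complications, serious adverse events (SAE) and device-related adverse events (adverse device effect) must be recorded in the CRF". It then adds: "Additional reporting criteria are listed under 7.3 Adverse event reporting". Section 7.3.1 widens the scope: "procedure-related adverse events, and adverse device effects related to Perclose SMC must be reported". The 6.7 schedule ticks adverse events and concomitant medications at 30 days, in a column headed as an office visit. Under 10.8, the Clinical Events Committee (CEC) adjudicates the 4.2 events that investigators report or safety personnel identify.

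**The concern.** Infection and nerve injury at a groin access site can appear after the patient has gone home. Section 6.5 treats both as important enough to require a visit when present at discharge, then leaves them out of the only question it specifies for telephoned subjects. A caller who follows the text would ask about vascular signals and could end the call there.

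The events at risk include some that the plan itself grades major. An infection treated with oral antibiotics, or a lasting sensory deficit, need not meet any criterion in 7.1.2, so serious-event reporting does not reliably bring it in. If the subject does not mention it, the site has nothing to report and the CEC nothing to adjudicate. In a small descriptive safety study, a count of zero is informative only if the question was asked.

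**Working it through.** **Inputs.** Sample size: "A total of 35 subjects will be registered in the clinical study" (5.6). Contact window: 30 ± 7 days, so day 23 to day 37 (6.5). Telephone eligibility: 6.5. Grades: 4.2. The documents give no expected discharge complication rate and no expected rate of infection or nerve injury, so there is no figure of the plan's own to reproduce.

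**Step 1: which sense of vascular complication governs the call?**
- 6.5: the eligibility sentence, shortly before the telephone question, lists vascular complication, nerve injury and infection as three separate things (narrow sense).
- 10.8: the 4.2 endpoint events are described as vascular complications together with other access site-related complications (narrow sense).
- 4.2: infection, nerve injury and pulmonary embolism appear in a list introduced as vascular complications (wide sense).

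The term is used in two senses. Read within its own section, the 6.5 question takes the narrow one.

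**Step 2: reporting against eliciting.** Section 7.0 alone omits procedure-related events, but it refers on to 7.3, and 7.3.1 includes them with no seriousness limit, up to the 30-day follow-up. Take a groin infection on day 10, treated with oral antibiotics and attributed to the puncture rather than the device. Once known, it is reportable. What the text lacks is a prompt that makes it known during a call. The adverse-event tick in 6.7 does not clearly supply one, because its column is headed as an office visit. The medication tick helps little, because 6.1.2 covers anticoagulants and antiplatelets, not antibiotics.

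**Step 3: how many subjects could be telephoned?** Let p be the share with a vascular complication, nerve injury or infection at discharge (assumed). Expected number eligible = 35 × (1 − p). The last column is the binomial probability that at least 18 of 35 are eligible.

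| p (assumed) | 35 × (1 − p) | P(at least 18 of 35) |
|---|---|---|
| 5% | 33.3 | > 0.99 |
| 10% | 31.5 | > 0.99 |
| 20% | 28.0 | > 0.99 |
| 30% | 24.5 | 0.99 |
| 40% | 21.0 | 0.89 |
| 50% | 17.5 | 0.50 |

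A majority is likely if p is clearly below 50%, but the documents do not establish that. The table counts people who may be telephoned, not events missed.

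**Step 4: size of one missed event.** 1/35 = 2.9%, so a miss turns 1/35 (2.9%) into 0/35 (0%). As an illustration with 28 telephoned subjects (p = 20%) and an assumed post-discharge event rate of 1% to 5%, the expected number of events is 28 × 0.01 = 0.28 to 28 × 0.05 = 1.4. The chance of at least one is 1 − 0.99^28 = 0.245 to 1 − 0.95^28 = 0.762. These are events occurring, hence an upper limit on events missed.

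**Step 5: timing of the nerve-injury grade.** Take the procedure as day 0 and count persistence from onset on day d. At the last permitted contact the injury has lasted 37 − d days, which exceeds 30 only if d < 7. At a contact on day 30 or earlier, no injury starting after the procedure can yet have lasted more than 30 days. The contact must therefore capture ongoing symptoms; the grade often cannot be settled at that point.

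**The case against.** The strongest reply is that the plan already covers these events. Section 7.3.1 requires procedure-related adverse events to be reported whatever their seriousness, 6.7 schedules adverse events at 30 days, and the lead-in to 4.2 lets infection and nerve injury count as vascular complications. Most of this stands. A reader who stops at the list in 7.0 might infer that non-serious procedure-related events need not be recorded; the referral to 7.3 rules that out. The 4.2 lead-in makes a wide reading of the telephone question possible, and Appendix II does not settle the matter, because its list of other access-site complications also contains vessel laceration and venous bleeding. But a duty to report does not bring out what a subject has not mentioned, and a term with two meanings is a poor basis for a telephone question.

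The case report forms (Appendix V) are not shown. The 30-day form may repeat the complication list, in which case the gap is in the text of 6.5 rather than in practice.

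A reader might also infer that ascertainment differs between visited and telephoned subjects. The documents do not show this: 6.5 gives no infection or nerve checklist for site visits either. Nor does holding the 6.4 checklist only at discharge mean that the rest of follow-up is unobserved, since adverse-event surveillance runs from first device insertion to the 30-day follow-up.

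Finally, the primary endpoint is ultrasound-detected complications, and there is no hypothesis test (8.6) or success criterion (8.7). That is correct and limits the consequence.

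**Conclusion.** The point holds as a gap in elicitation. Section 6.5 states a telephone question that, in the sense that section uses, leaves out two descriptive endpoints with non-serious major grades; 6.7 does not make clear that its adverse-event assessment applies to calls; and 7.0 and 7.3.1 describe the recording scope differently. In subjects followed by telephone, infection or nerve injury arising after discharge may therefore go unasked and not reach the CEC.

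Each missed event is worth 2.9 percentage points on a descriptive rate with 35 subjects. The primary endpoint does not change. The number telephoned is not stated: 28 to 31.5 expected at an assumed discharge rate of 20% to 10%, and 21 at 40%.

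A reader might go further and conclude that events will be missed in most subjects, or that the reported rates will be too low. The documents support neither: the first rests on an assumed discharge rate and confuses subjects called with events missed, and the second treats a possibility as an outcome. Pulmonary embolism is the weaker example, since it will often qualify as a serious adverse event.

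**What to change.** - **6.5:** state that the 30-day contact, by telephone or visit, goes through the existing 6.4 access-site complication list, including infection (with antibiotic use), nerve symptoms and pulmonary embolism, and that the answers, including negative ones, are recorded in the eCRF. Using one list for both modes also removes the ambiguity about what counts as vascular.
- **6.7:** relabel the 30-day column so that it covers an office visit or a telephone contact.
- **7.0:** name procedure-related adverse events, so that its scope matches 7.3.1.
- **Analysis rule (optional, from Step 5):** state how a nerve injury still present at the last contact is classified when 30 days from onset have not yet passed.

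The list already exists, so the cost is a short call script, a column label and a sentence in 7.0. The downside is a few minutes per call and possibly a few more minor events reported.
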